5.8. Software

All analyses will be carried out using validated software, e.g. SAS version 9.4 or upgrades.

¹ Note that all data can be changed based on query management before CDMS closure.

6. Specific Study Dates

6.1. Enrollment date

CIP chapter 8.8.5 Point of enrollment and study termination

The point of enrollment is defined as the date of signature of the informed consent form by the patient. Study related procedures, documentation and collection/following of adverse events will start from this day on.

Data file, unique identifier patient_display_id_full	Variable name	Variable label	Variable level	Nominal values
enrollment	dmicdtc	Patient: Date of IC signature	date	n.a.

6.2. Implantation Date

Data file, unique identifier patient_display_id_full	Variable name	Variable label	Variable level	Nominal values
implantation_general_data	imp_visdate	Date of implantation of Ilivia and Plexa	date	n.a.

6.3. Termination Date

CIP chapter 8.8.5 Point of enrollment and study termination

The point of study termination is defined as date of 6-month follow-up for patients with regular study termination. For a non-regular study termination, the following rules apply:

- If none of the investigational devices could successfully be implanted, date of study termination should be the date of the last unsuccessful implantation attempt.
- In case of replacement or repositioning of the Plexa ICD lead in patients of Group B date of study termination should be date of revision.
- In case of withdrawal of a patient's consent, date of study termination should be the date of withdrawal of consent.
- In case of patient death, the date of study termination should be the date of the patient's death.
- If patient is lost to follow-up, date of termination should be the date of last contact of the physician to the patient.
- If patient is defined as drop-out patient for any other reason, date of study termination should be the date of latest medical information of the patient (e.g. follow-up, IEGM).

Ilivia Termination Date

Data file, identifier patient_display_id_full	Variable name	Variable label	Variable level	Nominal values
study_termination	end_visdate	Date of study termination	date	n.a.
study_termination	end_group_term	Was group participation in one of the groups already terminated before the overall termination date?	nominal	No Yes, group A terminated Yes, group B terminated
study_termination	end_group_term_date	Date of group specific termination	date	n.a.
data_SAR	enddate_Ilivia_SAR ²	Date of Ilivia study termination	date	n.a.

Plexa Termination Date

Data file, identifier patient_display_id_full	Variable name	Variable label	Variable level	Nominal values
data_SAR	enddate_Plexa_SAR ³	Date of Plexa study termination	date	n.a.

7. Analysis Sets

7.1. Full Analysis Set

Data file, identifier patient_display_id_full	Variable name	Variable label	Variable level	Nominal values
enrollment	DMSUBIC	Patient has provided written informed consent	nominal	Yes /No
data_SAR	analysis_set_full_SAR ⁴	Full analysis set	nominal	Yes / No

² IF end_group_term = Yes, group A terminated
THEN enddate_Ilivia_SAR = end_group_term_date
ELSE enddate_Ilivia_SAR = end_visdate

³ IF end_group_term = Yes, group B terminated
THEN enddate_Plexa_SAR = end_group_term_date
ELSE enddate_Plexa_SAR = end_visdate

⁴ IF DMSUBIC = Yes
THEN analysis_set_full_SAR = Yes
ELSE analysis_set_full_SAR = No

All rights pertaining to this document are exclusively held by BIOTRONIK SE & Co. KG. Any non-authorized copying, reproduction or distribution is not permitted. Confidentiality: This document and/or its contents are only for internal use.

7.2. Ilivia Analysis Set

The analysis set Ilivia consists of all patients in group A and in group AB, who met all in- and exclusion criteria. Patients who did not come in contact with any Ilivia device are not included in the analysis set.

Data file, identifier patient_display_id_full	Variable name	Variable label	Variable level	Nominal values
enrollment	DMSUBIC	Patient has provided written informed consent	nominal	Yes /No
enrollment	TIINCL01 TIINCL02 TIINCL03 TIINCL04 TIINCL05 TIINCL06	Inclusion criteria [...]	nominal	Yes /No
enrollment	TIEXCL01 TIEXCL02 TIEXCL03 TIEXCL04 TIEXCL05 TIEXCL06 TIEXCL07	Exclusion criteria [...]	nominal	Yes /No
implantation_general_data	imp_group	Patient Group		Device of the Ilivia family (group A) Plexa right ventricular lead (group B) Both Ilivia and Plexa (group AB)
study_termination	end_early_a	Reason for early study termination	nominal	Implantation of Ilivia ICD family was planned but not performed (patient did not come in contact with the investigational device) [...]
study_termination	end_early_ab	Reason for early study termination	nominal	Implantation of Ilivia ICD family and Plexa lead were planned but not performed (patient did not come in contact with the investigational devices) [...]
data_SAR	analysis_set_Ilivia_SAR ⁵	Analysis set Ilivia	nominal	Yes / No

A list of all patients with early drop-out with patient ID, patient group and reason for early study termination will be provided.

⁵ IF DMSUBIC = Yes AND
TIINCL01 = Yes AND TIINCL02 = Yes AND TIINCL03 = Yes AND
TIINCL04 = Yes AND TIINCL05 = Yes AND TIINCL06 = Yes AND
TIEXCL01 = No AND TIEXCL02 = No AND TIEXCL03 = No AND
TIEXCL04 = No AND TIEXCL05 = No AND TIEXCL06 = No AND TIEXCL07 = No AND
(imp_group = ... (group A) OR imp_group = ... (group AB)) AND
end_early_a ≠ Implantation of Ilivia ICD family was planned but not performed ... AND
end_early_ab ≠ Implantation of Ilivia ICD family and Plexa lead were planned but not performed ...
THEN analysis_set_Ilivia_SAR = Yes
ELSE analysis_set_Ilivia_SAR = No

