11.7 Termination criteria

Group A of the clinical investigation will be terminated after confirmed knowledge of at least 4 patients with one or more Ilivia-endpoint-related SAEs (see 18.11), because it would be impossible to accept the primary Alternative hypothesis 1 for the planned sample size.

Group B of the clinical investigation will be terminated after confirmed knowledge of at least 9 (or at least 10 in case of a low dropout rate) patients with one or more Plexa-endpoint-related SAEs (see 18.11), because it would be impossible to accept the primary Alternative hypothesis 2 for the planned sample size.

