18.11 Definition of endpoint-related SADEs

The SADE-free rate calculated for primary endpoint 1 of the Ilivia family and primary endpoint 2 for the Plexa ICD lead will be based on the total number of subjects with at least one SADE related to the respective device.

Endpoint-related SADEs are complications, which are device-related adverse events that are corrected using invasive measures or require invasive measures to correct or which result in the loss of significant device function (e.g. lead dislodgement). Device-related adverse events, which are corrected by non-invasive measures (e.g. reprogramming) are considered observations and will not contribute to the primary endpoints.

Only SADEs directly related to the device in question (SADE-d) will be included in the endpoint. SADEs which are securely related to the implantation procedure (SADE-p) (e.g. pocket infection, etc.) will not be considered for the primary endpoints. Furthermore lead infections

will not be considered for the endpoint as long as the specific event cannot be securely classified as related to the investigational device. Inappropriate ICD therapies which are not related to a device defect (e.g. correct sensing and behavior of the device according to device specification) will also not be considered for primary endpoint analysis. Furthermore twiddler`s syndrome will not be considered for the endpoint analysis.

All serious adverse device effects that meet these primary endpoint criteria for the respective device will be included in the primary endpoint event analysis, respectively. Adverse events with a device relation of "not related" will not contribute to or be included in the evaluation of the primary safety endpoints of both devices.

The SADEs will be adjudicated by an internal adjudication board, whereby the seriousness and device relatedness will be re-examined.

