7.3. Plexa Analysis Set

Similar to the definition of the Ilivia analysis set (see chapter 7.2), the Plexa analysis set consists of all patients in group B and in group AB, who met all in- and exclusion criteria. Patients who did not come in contact with any Plexa lead are not included in the analysis set.

Data file, identifier patient_display_id_full	Variable name	Variable label	Variable level	Nominal values
enrollment	DMSUBIC	Patient has provided written informed consent	nominal	Yes /No
enrollment	TIINCL01 TIINCL02 TIINCL03 TIINCL04 TIINCL05 TIINCL06	Inclusion criteria [...]	nominal	Yes /No
enrollment	TIEXCL01 TIEXCL02 TIEXCL03 TIEXCL04 TIEXCL05 TIEXCL06 TIEXCL07	Exclusion criteria [...]	nominal	Yes /No
implantation_gene ral_data	imp_group	Patient Group		Device of the Ilivia family (group A) Plexa right ventricular lead (group B) Both Ilivia and Plexa (group AB)
study_termination	end_early_b	Reason for early study termination	nominal	Implantation of Plexa lead was planned but not performed (patient did not come in contact with the investigational device) [...]
study_termination	end_early_ab	Reason for early study termination	nominal	Implantation of Ilivia ICD family and Plexa lead were planned but not performed (patient did not come in contact with the investigational devices) [...]
data_SAR	analysis_set_Plexa_ SAR ⁶	Analysis set Plexa	nominal	Yes / No

⁶ IF DMSUBIC = Yes AND
 TIINCL01 = Yes AND TIINCL02 = Yes AND TIINCL03 = Yes AND
 TIINCL04 = Yes AND TIINCL05 = Yes AND TIINCL06 = Yes AND
 TIEXCL01 = No AND TIEXCL02 = No AND TIEXCL03 = No AND
 TIEXCL04 = No AND TIEXCL05 = No AND TIEXCL06 = No AND TIEXCL07 = No AND
 (imp_group = ... (group B) OR imp_group = ... (group AB)) AND
 end_early_b ≠ Implantation of Plexa lead was planned but not performed ... AND
 end_early_ab ≠ Implantation of Ilivia ICD family and Plexa lead were planned but not performed ...
 THEN analysis_set_Plexa_SAR = Yes
 ELSE analysis_set_Plexa_SAR = No

8. General data

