16.1. Analysis set

CIP chapter 11.1. Statistical design, methods and analytical procedures

All endpoints are analysed per-protocol (PP), whereby the analysis sets are defined for each hypothesis separately.

CIP chapter 8.1 General considerations

Tab. 4: Required visit windows (1 month is defined as 30 days)

	Window	Days post-implant
3 months post-implant	± 30 days	61 to 121

All analyses are performed for a subset of the Ilivia analysis set. To avoid an over-estimation of the SADE-free rate, patients with premature study termination less or equal 60 days after implantation are excluded from the analysis set if no primary endpoint occurred.

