⁷² IF analysis_set_Ilivia_SAR = Yes AND
date_1stIliviaSADE_SAR - imp_visdate ≤ 60days OR enddate_Ilivia_SAR - imp_visdate ≥ 61 days
THEN Ilivia_primEP_analysis_set_SAR = Yes
ELSE Ilivia_primEP_analysis_set_SAR = No

⁷³ IF analysis_set_Ilivia_SAR = Yes AND
date_1stIliviaSADE_SAR ≠ missing AND
{[fu3_visdate ≠ missing AND fu3_visdate is compliant AND date_1st_IliviaSADE_SAR ≤ fu3_visdate] OR
[fu3_visdate ≠ missing AND fu3_visdate is not compliant
AND date_1st_IliviaSADE_SAR - imp_visdate ≤ 121 days] OR
[fu3_visdate = missing AND date_1stIliviaSADE_SAR - imp_visdate ≤ 121days] }
THEN Ilivia_primEP_SAR = Yes
ELSE Ilivia_primEP_SAR = No

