23.1. Analysis set

All analyses are performed for the Plexa analysis set⁹⁶.

CIP chapter 11.1 Statistical design, methods and analytical procedures

All endpoints are analysed per-protocol (PP), whereby the analysis sets are defined for each hypothesis separately.

CIP chapter 8.1 General considerations

Tab. 4: Required visit windows (1 month is defined as 30 days)

	Window	Days post-implant
3 months post-implant	± 30 days	61 to 121

All analyses are performed for a subset of the Plexa analysis set. To avoid an over-estimation of the SADE-free rate, patients with premature study termination less or equal 60 days after implantation are excluded from the analysis set if no primary endpoint occurred.

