date_1stPlexaSADE_SAR - imp_visdate ≤ 60 days OR enddate_Plexa_SAR - imp_visdate ≥ 61 days
THEN Plexa_primEP_analysis_set_SAR = Yes
ELSE Plexa_primEP_analysis_set_SAR = No

¹⁰⁰ IF analysis_set_Plexa_SAR = Yes AND
date_1stPlexaSADE_SAR ≠ missing AND
{ [fu3_visdate ≠ missing AND fu3_visdate is compliant AND date_1stPlexa_SADE_SAR ≤ fu3_visdate] OR
[fu3_visdate ≠ missing AND fu3_visdate is not compliant
AND date_1stPlexaSADE_SAR - imp_visdate ≤ 121 days] OR
[fu3_visdate = missing AND date_1stPlexaSADE_SAR - imp_visdate ≤ 121 days] }
THEN Plexa_primEP_SAR = Yes
ELSE Plexa_primEP_SAR = No

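### No planned SADE-free rate covers all consented patients exposed to the device: both primary tests and both Kaplan-Meier alternatives keep only fully eligible patients

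*SAP*

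**What the plan says.** The base sets are filtered on eligibility. For group A, "The analysis set Ilivia consists of all patients in group A and in group AB, who met all in- and exclusion criteria"; for group B, "the Plexa analysis set consists of all patients in group B and in group AB, who met all in- and exclusion criteria". SAP footnotes 5 and 6 code this as every inclusion item = Yes and every exclusion item = No, together with consent, group and device contact.

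The filter carries through to every SADE rate:
- Primary tests: "All analyses are performed for a subset of the Ilivia analysis set" (SAP 16.1) and "All analyses are performed for a subset of the Plexa analysis set" (SAP 23.1). Event-free patients who terminate by day 60 are also removed.
- Event variables: footnotes 73 and 100 set the endpoint to Yes only for members of the filtered sets.
- Kaplan-Meier alternatives (SAP 16.7, 23.7): all patients of the same two sets. They bring back the early terminators but not the ineligible patients.

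The consent-only full analysis set (SAP 7.1) is used only in SAP chapter 8, where the one event rate is mortality. Protocol 8.4 promises descriptive collection of adverse events. Apart from the endpoint chapters, mortality and one MRI item, however, SAP chapters 8 to 25 plan no adverse event or SADE table.

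Membership of the primary test sets is coded without brackets. After the set condition and an AND, footnote 72 continues "date_1stIliviaSADE_SAR - imp_visdate ≤ 60days OR enddate_Ilivia_SAR - imp_visdate ≥ 61 days" and footnote 99 continues "date_1stPlexaSADE_SAR - imp_visdate ≤ 60 days OR enddate_Plexa_SAR - imp_visdate ≥ 61 days".

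Protocol 11.7 sets a termination count: "Group A of the clinical investigation will be terminated after confirmed knowledge of at least 4 patients with one or more Ilivia-endpoint-related SAEs". It refers to Protocol 18.11 for the event and does not name an analysis set.

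**The concern.** Protocol 7.1 gives the aim as finding and evaluating residual risks of using the two devices. Exposure decides who can show such a risk, not whether every eligibility item was met. Eligibility is checked at enrolment (Protocol 9.2), but a breach found later is not among the mandatory drop-out reasons in Protocol 8.8.4.1. An implanted ineligible patient can therefore stay in follow-up, have an adjudicated device-related SADE, and appear in no planned rate.

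The tests allow few events, so one omitted patient could decide a verdict without any planned analysis giving the rate with that patient included. The unbracketed OR is a separate coding risk in the same variables: it could put patients into the denominator who cannot contribute an event.

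**Working it through.** **Inputs.** Null SADE-free rate 90% (Protocol 8.3.1.1, 8.3.1.2). Planning rates 98% (A) and 97% (B), analysed n = 94 and 166, enrolled 105 and 185 (Protocol 11.2). One-sided level 1.25% (Protocol 11.3). Two-sided 97.5% interval (SAP 16.6, 23.6).

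**1. The plan's own figures.** The test passes with x SADE patients among n if P(X ≤ x | n, 0.10) ≤ 0.0125.
- A, n = 94: at most 3 SADE patients; exact level 0.01246; power 88.0% at 98%.
- B, n = 166: at most 8; exact level 0.01215; power 93.6% at 97%.
- With 10% drop-out: 94/0.9 = 104.4, so 105; 166/0.9 = 184.4, so 185.

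The sample sizes reproduce. The limit stays at 3 for n = 94-109 and at 8 for n = 166-179. The termination counts in Protocol 11.7 (4; 9, or 10 with low drop-out) agree with these limits.

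**2. One exposed ineligible patient with a SADE, at the boundary.**

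| Group | Set | SADE/n | p | Lower 97.5% limit | Result |
|---|---|---|---|---|---|
| A | per-protocol | 3/94 | 0.0125 | just above 90.0% | pass |
| A | all exposed | 4/95 | 0.033 | 88.6% | fail |
| B | per-protocol | 8/166 | 0.012 | just above 90.0% | pass |
| B | all exposed | 9/167 | 0.025 | 89.3% | fail |

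**3. How likely this is.** The documents give no breach rate. Assume m = 1 to 5 ineligible exposed patients with the same SADE probability q as the others. Let c be the pass limit (3 or 8), which is the same at n and n + m here. Then

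P(per-protocol pass, all-exposed fail) = Σ over x ≤ c of P(X = x | n, q) × P(Y > c − x | m, q).

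For m = 1 only x = c contributes. Group A: P(X = 3 | 94, 0.02) × 0.02 = 0.1706 × 0.02 = 0.0034. Group B: P(X = 8 | 166, 0.03) × 0.03 = 0.0642 × 0.03 = 0.0019.

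| Group | q | m = 1 | m = 2 | m = 3 | m = 5 |
|---|---|---|---|---|---|
| A | 2% | 0.3% | 0.7% | 1.0% | 1.8% |
| A | 5% | 0.8% | 1.6% | 2.3% | 3.8% |
| B | 3% | 0.2% | 0.4% | 0.6% | 1.0% |
| B | 5% | 0.7% | 1.4% | 2.1% | 3.5% |

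Expected SADE patients left out at the planning rates are m × q: 0.02 to 0.10 (A) and 0.03 to 0.15 (B).

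**4. The unbracketed OR.** If AND binds before OR, footnote 72 admits anyone whose Ilivia end date is at least 61 days after implantation, whether or not in the Ilivia set. Footnote 2 gives every patient such a date: the overall termination date applies unless group A was terminated earlier. So patients enrolled only in group B would enter the Ilivia denominator, and footnote 73 would force their endpoint to No. Footnotes 3, 99 and 100 do the same with group-A-only patients for Plexa.

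The overlap k of the groups is not given; at planned enrolment it can lie between 0 and 105. Group-B-only patients then number 185 − k, that is 80 to 185, and group-A-only patients 105 − k, that is 0 to 105, before drop-out. All who are followed for 61 days or more would count as event-free, so the SADE-free rate is biased upward by an amount that depends on k.

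**The case against.** The strongest reply is that the plan does what it announced. Protocol 11.1 pre-specifies per-protocol analysis with sets defined for each hypothesis, and the SAP implements this openly. That stands: the primary set is not an error.

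A reader might infer a contradiction with Protocol 18.11, which says "All serious adverse device effects that meet these primary endpoint criteria for the respective device will be included in the primary endpoint event analysis" and names no eligibility condition. The documents do not support that reading. Section 18.11 defines which events qualify; the population comes from Protocol 8.3.1, which divides by the patients in the analysis set, and from 11.1.

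A reader might also infer that a failing result would be hidden. That goes too far. If Protocol 11.7 counts patients regardless of eligibility, the fourth SADE patient in group A, or the ninth in group B (tenth with low drop-out), could surface through that count. Deviations go into the investigation reports (Protocol 14.2.3) and adverse events are to be collected descriptively. These routes give visibility but no rate.

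Leaving out an event-free patient can act the other way: 3/93 gives p = 0.0134 and 8/165 gives p = 0.0129, both fails. But these cases sit exactly on a step of the pass limit and do not show general fragility.

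On the brackets, the text of SAP 16.1 and 23.1 makes the intended subset clear, so only a literal coding would go wrong. One might size that fault by adding a single ineligible patient to the denominator; this understates it, because patients of the other group would enter too.

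**Conclusion.** The point holds as a gap in supportive analysis, not as a fault in the primary test. No planned SADE rate covers all consented patients exposed to the device. The expected effect is small: 0.3-1.8% (A) and 0.2-1.0% (B) for a per-protocol pass that is an all-exposed fail, assuming 1 to 5 ineligible exposed patients, equal risk, the planning rates and per-protocol n of 94 and 166. At a true 95% rate the figures are 0.8-3.8% and 0.7-3.5%.

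The direction is unknown, because nothing in the documents shows that ineligible patients carry more or less device risk. A claim of type I error inflation would not be supported; at equal risk there is none. The case for acting rests on the study aim, the narrow pass limits and the low cost.

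The missing brackets are a real error in the written rule. Their effect cannot be sized from the documents because the group overlap is not given.

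**What to change.** 1. In SAP 16 and 23 add, as supportive only, the SADE-free rate with exact two-sided 97.5% interval and the Kaplan-Meier estimate in all consented patients of the group who had contact with the device. The set is footnotes 5 and 6 without the TIINCL and TIEXCL lines, carried into footnotes 72/73 and 99/100. State that the Kaplan-Meier estimate also covers event-free patients who terminate by day 60, whom the exact analysis still omits. List every endpoint SADE in excluded exposed patients, with the criterion breached and the relatedness.
2. In footnotes 72 and 99, put brackets around the two conditions (first SADE by day 60 OR termination at day 61 or later) and join the bracket by AND to set membership.
3. State whether the Protocol 11.7 count uses the same population as the tested count, and reconcile the two if it does not.

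The cost is SAP wording, one flag and one more run of existing code. The primary set, significance level and sample size do not change. The downside is that a few ineligible patients enter the supportive analysis. In group B some of their events may not be attributable between an old right ventricular lead and Plexa (Protocol 8.8.2, footnote h), which is why the listing should show criterion and relatedness.

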7.3. Plexa Analysis Set

Similar to the definition of the Ilivia analysis set (see chapter 7.2), the Plexa analysis set consists of all patients in group B and in group AB, who met all in- and exclusion criteria. Patients who did not come in contact with any Plexa lead are not included in the analysis set.

Data file, identifier patient_display_id_full	Variable name	Variable label	Variable level	Nominal values
enrollment	DMSUBIC	Patient has provided written informed consent	nominal	Yes /No
enrollment	TIINCL01 TIINCL02 TIINCL03 TIINCL04 TIINCL05 TIINCL06	Inclusion criteria [...]	nominal	Yes /No
enrollment	TIEXCL01 TIEXCL02 TIEXCL03 TIEXCL04 TIEXCL05 TIEXCL06 TIEXCL07	Exclusion criteria [...]	nominal	Yes /No
implantation_gene ral_data	imp_group	Patient Group		Device of the Ilivia family (group A) Plexa right ventricular lead (group B) Both Ilivia and Plexa (group AB)
study_termination	end_early_b	Reason for early study termination	nominal	Implantation of Plexa lead was planned but not performed (patient did not come in contact with the investigational device) [...]
study_termination	end_early_ab	Reason for early study termination	nominal	Implantation of Ilivia ICD family and Plexa lead were planned but not performed (patient did not come in contact with the investigational devices) [...]
data_SAR	analysis_set_Plexa_ SAR ⁶	Analysis set Plexa	nominal	Yes / No

⁶ IF DMSUBIC = Yes AND
 TIINCL01 = Yes AND TIINCL02 = Yes AND TIINCL03 = Yes AND
 TIINCL04 = Yes AND TIINCL05 = Yes AND TIINCL06 = Yes AND
 TIEXCL01 = No AND TIEXCL02 = No AND TIEXCL03 = No AND
 TIEXCL04 = No AND TIEXCL05 = No AND TIEXCL06 = No AND TIEXCL07 = No AND
 (imp_group = ... (group B) OR imp_group = ... (group AB)) AND
 end_early_b ≠ Implantation of Plexa lead was planned but not performed ... AND
 end_early_ab ≠ Implantation of Ilivia ICD family and Plexa lead were planned but not performed ...
 THEN analysis_set_Plexa_SAR = Yes
 ELSE analysis_set_Plexa_SAR = No

8. General data

